5. STUDY DESIGN

Study GZHA is a Phase 1, single-site, randomized, placebo controlled, single-ascending dose (SAD) study in healthy participants, to evaluate the safety, tolerability, and PK of LY3493269 administered as single SC doses and as a single IV dose. The PD effects of SC doses of LY3493269 on glycemic effects (including fasting glucose, insulin, and glucose and insulin during an oral glucose tolerance test [OGTT]) and appetite will be explored. For the SC cohorts, the investigator and participants will be blinded. The IV Cohort is open label with no placebo.

The planned LY3493269 SC doses for this study range from 0.15 mg to 7.5 mg. These dose levels may be adjusted (for example, dose increments may be reduced, a dose level may be repeated, or a lower/intermediate dose may be administered) based on ongoing review of available safety, tolerability, PK, and PD data. Any proposal to adjust SC or IV doses from those planned and stated in the protocol, together with supporting data, will be reviewed by an independent safety review panel.

Participants will undergo safety (including but not limited to adverse events [AEs], medical assessments, clinical laboratory tests, body weight, vital signs and ECGs]), PK and PD assessments.

Subcutaneous Administration Cohorts 1 through 6

This study includes up to 6 planned SC cohorts:

- SC Cohort 1: 0.15 mg (6 LY3493269: 2 Placebo)
- SC Cohort 2: 0.5 mg (6 LY3493269: 2 Placebo)
- SC Cohort 3: 1.5 mg (6 LY3493269: 2 Placebo)
- SC Cohort 4: 3.0 mg (6 LY3493269: 2 Placebo)
- SC Cohort 5: 5.0 mg (6 LY3493269: 2 Placebo)
- SC Cohort 6: 7.5 mg (6 LY3493269: 2 Placebo)

Cohorts 2 to 6 will be initiated only if the investigator and Eli Lilly and Company clinical pharmacologist deem the safety results in the preceding cohort to be acceptable through Day 8 from at least 6 participants dosed. In addition, all planned participants in the current cohort should have been dosed prior to escalation to the next cohort.

Intravenous Administration Cohort

This study includes a single IV cohort (IV Cohort), where up to 6 healthy participants should complete dosing at the same level to provide sufficient PK sampling. The IV Cohort will be initiated based on review of safety and tolerability data from SC Cohort 3 and available 7-day PK data and/or PD data from at least 2 preceding SC cohorts.

All participants will receive LY3493269 only (that is no placebo group), as a single IV bolus dose. The planned dose is 0.5 mg. This dose is expected to be safe while providing plasma concentrations that can be adequately measured over the sampling time period enabling adequate characterization of the PK profile. The IV dose may be increased to a maximum of 1.5 mg or

decreased to a minimum of 0.25 mg depending on emerging data. It is intended that the IV dose will be administered sequentially, with 1 participant having completed the dosing and observed for at least 20 minutes before the next participant is dosed.

In the IV Cohort, 2 participants will initially receive the planned 0.5 mg dose. An additional 4 participants will receive investigational product following joint investigator and sponsor review of safety and tolerability data through at least 4 days postdose (including Day 5 safety labs and assessments) from the 2 initial participants.

Figure GZHA.1 illustrates the study design.

Abbreviations: IV = intravenous; LY = LY3493269; PL = Placebo; SC = subcutaneous.

6. TREATMENTS

The following is a list of the study treatment abbreviations that will be used in the TFLs.

Study Treatment Name	Treatment order in TFL
Placebo SC	1
0.15 mg LY3493269 SC	2
0.5 mg LY3493269 SC	3
0.5 mg LY3493269 IV	4
1.5 mg LY3493269 SC	5
3.0 mg LY3493269 SC	6
5.0 mg LY3493269 SC	7

8

7.5 mg LY3493269 SC

7. SAMPLE SIZE JUSTIFICATION

Up to 70 participants may be enrolled so that approximately 54 participants complete the study.

The sample size is customary for Phase 1 studies evaluating safety and PK and is not powered on the basis of statistical hypothesis testing.

Participants who are randomized but not administered treatment prior to discontinuation may be replaced to ensure that approximately 8 participants complete each SC Cohort, and 6 to complete the IV cohort.

Participants who discontinue early mat be replaced after consultation with the investigator and sponsor. The replacement participant will be assigned to the same treatment as the discontinued participant.

8. DEFINITION OF ANALYSIS POPULATIONS

The "Safety" population will consist of all subjects who received at least one dose of study drug or placebo.

The "Pharmacokinetic" population will consist of all subjects who received at least one dose of study drug and have evaluable PK data.

The "Pharmacodynamic" population will consist of all subjects who received at least one dose of study drug or placebo and have evaluable PD data.

All protocol deviations that occur during the study will be considered for their severity/impact and will be taken into consideration when subjects are assigned to analysis populations.

9. STATISTICAL METHODOLOGY

9.1 General

Data listings will be provided for all data that is databased. Summary statistics and statistical analysis will only be presented for data where detailed in this SAP. For continuous data, summary statistics will include the arithmetic mean, arithmetic standard deviation (SD), median, min, max and N; for log-normal data (e.g. the PK parameters: area under the concentration versus time curve [AUCs] and maximum observed drug concentration [C_{max}]) the geometric mean and geometric coefficient of variation (CV%) will also be presented. For categorical data, frequency count and percentages will be presented. Data listings will be provided for all subjects up to the point of withdrawal, with any subjects excluded from the relevant population highlighted. Summary statistics and statistical analyses will generally only be performed for subjects included in the relevant analysis population. For the calculation of summary statistics and statistical analysis, unrounded data will be used.

Mean change from baseline is the mean of all individual subjects' change from baseline values. Each individual change from baseline will be calculated by subtracting the individual subject's baseline value from the value at the timepoint. The individual subject's change from baseline values will be used to calculate the mean change from baseline using a SAS procedure such as Proc Univariate.

Data analysis will be performed using SAS[®] Version 9.4 or greater.

9.2 Demographics and Subject Disposition

Subject disposition will be listed. The demographic variables age, sex, race, ethnicity, body weight, height and body mass index will be summarized and listed. All other demographic variables will be listed only.

9.3 Pharmacokinetic Assessment

9.3.1 Pharmacokinetic Analysis

PK parameter estimates will be determined using non-compartmental procedures in validated software program (Phoenix WinNonlin Version 8.1 or later).

Plasma concentrations of LY3493269 will be used to determine the following PK parameters, when possible:

Statistical Analysis Plan Covance Clinical Study No. 1001215-8415534

Parameter	Units	Definition
AUC(0-t _{last})	h*ng/mL	area under the concentration versus time curve from time zero to time t, where t is the last time point with a measurable concentration
AUC(0-168 h)	h*ng/mL	area under the concentration versus time curve from time zero to 168 hours postdose
$AUC(0-\infty)$	h*ng/mL	area under the concentration versus time curve from time zero to infinity
$AUC(t_{last}-\infty)$	%	percentage of AUC($0-\infty$) extrapolated
C _{max}	ng/mL	maximum observed drug concentration
t _{max}	h	time of maximum observed drug concentration
t½	h	half-life associated with the terminal rate constant (λz) in non-compartmental analysis
CL	L/h	total body clearance of drug calculated after intravenous administration
CL/F	L/h	apparent total body clearance of drug calculated after extra-vascular administration
R _A	N/A	Accumulation ratio (AUC(0-∞))/AUC(0-168 h))
Vz	L	volume of distribution during the terminal phase after intravenous administration
V _Z /F	L	apparent volume of distribution during the terminal phase after extra-vascular administration
V _{ss}	L	volume of distribution at steady state after intravenous administration
V _{ss} /F	L	apparent volume of distribution at steady state after extra-vascular administration

Additional PK parameters may be calculated, as appropriate.

The software and version used for the final analyses will be specified in the clinical study report. Any exceptions or special handling of data will be clearly documented within the final study report.

Formatting of tables, figures and abbreviations will follow the Eli Lilly Global PK/PD/TS Tool: NON-COMPARTMENTAL PHARMACOKINETIC STYLE GUIDE. The version of the tool effective at the time of PK analysis will be followed.

General PK Parameter Rules

- Actual sampling times will be used in the final analyses of individual PK parameters, except for non-bolus pre-dose sampling times which will be set to zero.
- C_{max} and t_{max} will be reported from observed values. If C_{max} occurs at more than one time point, t_{max} will be assigned to the first occurrence of C_{max}.

- AUC parameters will be calculated using a combination of the linear and logarithmic trapezoidal methods (linear-log trapezoidal rule). The linear trapezoidal method will be applied up to t_{max} and then the logarithmic trapezoidal method will be used after t_{max}. The minimum requirement for the calculation of AUC will be the inclusion of at least three consecutive concentrations above the LLOQ, with at least one of these concentrations following C_{max}.
- AUC(0-∞) values where the percentage of the total area extrapolated is more than 20% will be flagged. Any AUC(0-∞) value excluded from summary statistics will be noted in the footnote of the summary table.
- Half-life $(t_{\frac{1}{2}})$ will be calculated, when appropriate, based on the apparent terminal log-linear portion of the concentration-time curve. The start of the terminal elimination phase for each subject will be defined by visual inspection and generally will be the first point at which there is no systematic deviation from the log-linear decline in plasma concentrations. Half-life will only be calculated when a reliable estimate for this parameter can be obtained comprising of at least 3 data points. If $t_{\frac{1}{2}}$ is estimated over a time window of less than 2 half-lives, the values will be flagged in the data listings. Any $t_{\frac{1}{2}}$ value excluded from summary statistics will be documented in the footnote of the summary table.
- A uniform weighting scheme will be used in the regression analysis of the terminal loglinear portion of the concentration-time curve.
- The parameters based on predicted last observed drug concentration will be reported.

Individual PK Parameter Rules

- Only quantifiable concentrations will be used to calculate PK parameters with the exception of special handling of certain concentrations reported below the lower limit of quantitation (BQL). Plasma concentrations reported as BQL will be set to a value of zero when all of the following conditions are met:
 - The compound is non-endogenous.
 - The samples are from the initial dose period for a subject or from a subsequent dose period following a suitable wash-out period.
 - \circ The time points occur before the first quantifiable concentration.
- All other BQL concentrations that do not meet the above criteria will be set to missing.
- Also, where two or more consecutive concentrations are BQL towards the end of a profile, the profile will be deemed to have terminated and therefore any further quantifiable concentrations will be set to missing for the calculation of the PK parameters unless it is considered to be a true characteristic of the profile of the drug.

• For multiple-dosing data, when pre-dose concentrations are missing, the value to be substituted will be the minimum observed drug concentration for the dosing interval.

Individual Concentration vs. Time Profiles

- Individual concentrations will be plotted utilizing actual sampling times.
- The terminal point selections will be indicated on a semi-logarithmic plot.

Average Concentration vs. Time Profiles

- The average concentration profiles will be graphed using scheduled (nominal) sampling times.
- The average concentration profiles will be graphed using arithmetic average concentrations.
- The pre-dose average concentration for single-dose data from non-endogenous compounds will be set to zero. Otherwise, only quantifiable concentrations will be used to calculate average concentrations.
- Concentrations at a sampling time exceeding the sampling time window specified in the protocol, or $\pm 10\%$, will be excluded from the average concentration profiles.
- Concentrations excluded from the mean calculation will be documented in the final study report.
- A concentration average will be plotted for a given sampling time only if 2/3 of the individual data at the time point have quantifiable measurements that are within the sampling time window specified in the protocol or ± 10%. An average concentration estimated with less than 2/3 but more than 3 data points may be displayed on the mean concentration plot if determined to be appropriate and will be documented within the final study report.

Treatment of Outliers during Pharmacokinetic Analysis

Application of this procedure to all PK analyses is not a requirement. Rather, this procedure provides justification for exclusion of data when scientifically appropriate. This procedure describes the methodology for identifying an individual value as an outlier for potential exclusion, but does not require that the value be excluded from analysis. The following methodology will not be used to exclude complete profiles from analysis.

Data within an Individual Profile

A value within an individual profile may be excluded from analysis if any of the following criteria are met:

- For PK profiles during single dosing of non-endogenous compounds, the concentration in a pre-dose sample is quantifiable.
- For any questionable datum that does not satisfy the above criteria, the profile will be evaluated and results reported with and without the suspected datum.

Data between Individual Profiles

- 1. If n < 6, then the dataset is too small to conduct a reliable range test. Data will be analyzed with and without the atypical value, and both sets of results will be reported.
- 2. If $n \ge 6$, then an objective outlier test will be used to compare the atypical value to other values included in that calculation:
 - a. Transform all values in the calculation to the logarithmic domain.
 - b. Find the most extreme value from the arithmetic mean of the log transformed values and exclude that value from the dataset.
 - c. Calculate the lower and upper bounds of the range defined by the arithmetic mean ± 3 *SD of the remaining log-transformed values.
 - d. If the extreme value is within the range of arithmetic mean ± 3 *SD, then it is not an outlier and will be retained in the dataset.
 - e. If the extreme value is outside the range of arithmetic mean ± 3 *SD, then it is an outlier and will be excluded from analysis.

If the remaining dataset contains another atypical datum suspected to be an outlier and $n \ge 6$ following the exclusion, then repeat step 2 above. This evaluation may be repeated as many times as necessary, excluding only one suspected outlier in each iteration, until all data remaining in the dataset fall within the range of arithmetic mean ± 3 *SD of the log-transformed values.

Reporting of Excluded Values

Individual values excluded as outliers will be documented in the final report. Approval of the final report will connote approval of the exclusion.

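### SAP 9.3.1 both requires and does not require exclusion of a flagged PK value, and at n of 6 or more it asks for no result with and without that value

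*SAP*

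**What the plan says.** All the rules on outliers are in SAP 9.3.1.

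- **Status of the procedure.** "Application of this procedure to all PK analyses is not a requirement". It offers a justification for exclusion when that is scientifically appropriate, and it "does not require that the value be excluded from analysis". Complete profiles may not be removed by it.
- **Between profiles, fewer than 6 values.** The SAP regards the set as too small for a reliable range test. "Data will be analyzed with and without the atypical value, and both sets of results will be reported".
- **Between profiles, 6 or more values.** Log-transform, set aside the most extreme value, and compute mean ± 3 SD from the rest. If the value lies outside, "then it is an outlier and will be excluded from analysis". The step may be repeated only while at least 6 values remain.
- **Reporting.** "Individual values excluded as outliers will be documented in the final report". Nothing further is required at 6 or more, and SAP 9.3.2 adds no sensitivity analysis.

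SAP 5 plans six active participants in every SC cohort, for example "SC Cohort 2: 0.5 mg (6 LY3493269: 2 Placebo", and up to six in the IV cohort. For AUC and Cmax, SAP 9.1 says that "the geometric mean and geometric coefficient of variation (CV%) will also be presented". SAP 9.3.2 uses the IV and corresponding SC geometric means to discuss absolute bioavailability and specifies no confidence interval for that comparison.

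**The concern.** Two analysts could follow this text and report different summaries from the same six values. One would treat step 2e as binding once the limit is crossed. The other would rely on the introduction and keep the value.

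The reporting rule also changes at an awkward place. With five values, the reader sees both results. With six, the limits are still computed from five values, but the reader need see only the result after exclusion and a note of what was removed. A complete active group in this trial has exactly six values.

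At stake are the group summaries of Cmax and AUC (secondary endpoints in protocol Section 4) and the SC and IV geometric means behind the bioavailability statement. A wrongly dropped value makes the drug look less variable than it is and shifts the geometric mean.

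**Working it through.** The SAP gives no error rate for its rule, so there is no figure of its own to reproduce. The size n = 6 is consistent with the planned total: 6 × 8 + 6 = 54 completers.

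**1. How often a clean group is flagged.** Inputs from SAP 9.3.1: n = 6, limit of 3 SD, mean and SD from the other five values. Assumption: normal log values with no true outlier. For any one value, (value − mean of others) / (SD of others × √(1 + 1/5)) follows a t distribution with 4 degrees of freedom.

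- Limit on the t scale: 3 / √1.2 = 2.739.
- P(|t₄| > 2.739) = 0.0520 per value.
- For the most extreme of six: 6 × 0.0520 = 0.312.

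Simulation of 1,000,000 groups agrees, at 31%. Other shapes give 23% (uniform), 36% (logistic) and 39% (t with 5 df). For comparison, a limit that flags 5% of clean normal groups of 6 would be about 5.3 SD.

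**2. What one dropped valid value does.** Dropping the extreme value moves the log mean by (extreme − mean of others) / 6. Geometric CV = 100 × √(exp(s²) − 1), where s is the log SD. The documents give no between-participant SD, so a range is shown. Results are for the flagged clean groups in the simulation:

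| Assumed log SD | True geometric CV | Median CV, all six | Median CV, value dropped | Mean shift in geometric mean |
|---|---|---|---|---|
| 0.2 | 20.2% | 18.8% | 9.8% | 7% |
| 0.3 | 30.7% | 28.5% | 14.8% | 11% |
| 0.5 | 53.3% | 49.3% | 25.0% | 19% |

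The reported CV is roughly halved. At log SD 0.3 the root-mean-square error of the log geometric mean rises from 0.123 to 0.163, a factor of 1.33. For bioavailability, a shift of 11% in one of the two geometric means turns a ratio of 100% into about 90% (1/1.11) or 111%.

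**3. Power model.** Six doses × 6 values, log SD 0.3, true proportionality, nominal 90% CI:

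- No exclusions: coverage 90.0%.
- Test run once on the 36 pooled dose-normalised values: about 90%.
- Test run within each cohort and exclusions carried into the model: 88.9% if a quarter of flags are dropped, 87.3% if half, 84.2% if all.

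The mean slope error is below 0.0004 in every cohort-level run, so the slope is not biased.

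**The case against.** **Step 2e applies only once someone has chosen to run the test.** On that reading the introduction governs and the conflict is narrow. This is partly right: the introduction makes use optional. But it also says that the procedure itself does not oblige exclusion, and step 2e says the opposite. The conflict remains, although a few words cure it.

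**The SAP's pattern is coherent.** A reader might infer that the SAP breaks its own within-profile rule, which says that "the profile will be evaluated and results reported with and without the suspected datum". The text does not support that. The within-profile rule covers only a questionable datum that does not meet the exclusion criterion; one that does meet it may be excluded without a second result. Only the rule for fewer than 6 values is a true parallel. Both-ways reporting at 6 or more is therefore an extension of that rule, justified by how loose the limit is at n = 6.

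**The 31% is not a forecast.** This stands. The test starts from a value already seen as atypical and its use is discretionary, so 31% bounds the share of clean groups losing a value under normal log values. At most one value can leave a group of 6.

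**The rule also catches real aberrations.** This stands too. One value truly shifted by 3 SD is correctly flagged 56% of the time, and by 4 SD 79%. That supports keeping the test as a flag.

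**A reader could recompute from the listings.** True for geometric means and CVs, since the data are listed and exclusions documented. But a report should show the effect of its own exclusions.

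**Conclusion.** Wrong as written, with low to moderate weight. The contradiction in SAP 9.3.1 is certain from the text. The missing comparison at 6 or more values matters because 3 SD from five values is not a rare-event limit. One valid value dropped from a group of 6 roughly halves the reported geometric CV and moves the geometric mean by about 11% (7% to 19% for log SD 0.2 to 0.5). The log SD and the normal shape are assumptions.

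Two stronger readings are not supported. The first is that the dose-proportionality interval loses coverage, to about 84%. That needs the test run in every cohort, every flag dropped, and those exclusions carried into the model. Step 2 compares a value with the others in the same calculation, which for the power model can be read as all SC active values; on pooled values the effect is negligible. The second is that statistical exclusion should be barred unless an error is documented. The SAP deliberately allows it when scientifically appropriate.

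The primary endpoints (TEAEs and SAEs) are unaffected, and no acceptance limit depends on the interval.

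**What to change.** In SAP 9.3.1:

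1. Reword the outcome in step 2e: *then it is flagged as a potential outlier and may be excluded when scientifically appropriate.*
2. Add: *For any n, if a value is excluded under this procedure, the PK summaries and any power-model or bioavailability result that uses it are reported with and without that value.*
3. Align the paragraph on repeating the test with this wording.

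Leave unchanged the separate SAP 9.3.1 provisions that let AUC(0-∞) and half-life values be left out of summary statistics with a footnote.

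The cost is a short text edit and one additional sensitivity table, needed only when an exclusion occurs.

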9.3.2 Pharmacokinetic Statistical Methodology

PK dose proportionality will be assessed. Log-transformed C_{max} , AUC(0-t_{last}) and AUC(0- ∞) of LY3493269 will be evaluated using a power model (where log-dose acts as an explanatory variable) to estimate ratios of dose-normalized geometric means and corresponding 90% confidence intervals (CIs). The estimated ratio of dose-normalized geometric means of PK parameters between the highest and lowest doses will be used to assess dose proportionality. A subinterval within the highest and lowest doses may also be considered for assessment of dose proportionality using the same approach.

A statistical analysis using the Kruskal-Wallis test³ will be conducted to investigate the dose proportionality (independence) of t_{max} . The p-value will be calculated for the overall dose comparison.

All PK parameters will be summarized using descriptive statistics. Geometric means of the IV dose group and corresponding SC dose group will be used to discuss absolute bioavailability.

Examples of the SAS code that will be used are as follows:

```
proc mixed data=xxx;
model log_pk = log_dose / alpha=0.1 cl solution outpred=resids ddfm=kr;
estimate 'xx mg' intercept 1 log_dose yy / alpha=0.1 cl; /*Log value of xx*/
estimate 'zz mg - xx mg' log_dose pp / alpha=0.1 cl; /*Difference in log
values of zz and xx*/
ods output solutionf=est;
ods output estimates=estims;
run;
```

Kruskal-Wallis Test

```
proc npar1way data=xxx
  class dose;
  var pk;
  output out=krusk;
run;
```

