#### 7.5. Dose Modification for Intravenous Cohort

If tolerability precludes dosing of the IV 0.5 mg cohort, the IV dose will be reduced to a minimum of 0.25 mg. Based on preclinical data, SC bioavailability for LY3493269 is expected to be close to 100%. If PK exposures from the SC 0.5 mg dose yields largely concentrations below quantification, the IV 0.5 mg dose is likely to be at risk for unmeasurable concentrations. Under such circumstances, the IV dose may be increased to a maximum of 1.5 mg and be initiated only after 7-day safety data is available from the SC 3.0 mg dose and 7-day PK data from at least 2 preceding SC cohorts. Any proposal to adjust IV doses from those planned and stated in the protocol, together with supporting data, will be reviewed by an independent SRP.

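### AUC(0-tlast) is in the dose-proportionality model although its time window can lengthen with dose; add the already derived AUC(0-168 h) and treat AUC(0-tlast) as supportive

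*SAP*

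**What the plan says.** SAP 9.3.2 names the parameters: log-transformed Cmax, AUC(0-tlast) and AUC(0-∞), which "will be evaluated using a power model (where log-dose acts as an explanatory variable"). The conclusion is to come from the top and bottom doses: "The estimated ratio of dose-normalized geometric means of PK parameters between the highest and lowest doses will be used to assess dose proportionality". The interval is a 90% CI. No acceptance range is given, and nothing says which AUC governs if the two disagree. Protocol 10.3.2.2 specifies the same model but says only Cmax and AUC.

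SAP 9.3.1 defines AUC(0-tlast) as the "area under the concentration versus time curve from time zero to time t, where t is the last time point with a measurable concentration". Values below the limit of quantitation are set to zero only before the first quantifiable sample; after that, "All other BQL concentrations that do not meet the above criteria will be set to missing". For AUC(0-∞), "values where the percentage of the total area extrapolated is more than 20% will be flagged", with no rule that requires exclusion. The same table lists a fixed-window parameter, the "area under the concentration versus time curve from time zero to 168 hours postdose". It is used in the accumulation ratio but does not appear in 9.3.2.

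The six planned SC doses run from 0.15 to 7.5 mg with six active participants each. SC sampling (Protocol Section 2) is predose, then 6, 12, 24, 48, 72, 96, 120 and 168 h, then Days 15, 29 and 43.

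**The concern.** A proportionality comparison needs the same quantity at every dose. When the profile at a low dose falls below the assay limit earlier than at a high dose, AUC(0-tlast) at the low dose omits area that the high dose includes. Late sampling is sparse: nominal times after 168 h are 336, 672 and 1008 h, so each lost sample removes one or two weeks of area. The error has one direction. The low-dose AUC is cut short, the log-log slope rises above 1, and a proportional drug can appear supra-proportional.

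At stake is the reading of a secondary PK objective. Protocol 5.4 says the data will help to choose dose ranges for later studies, including oral dosing, so a spurious departure from proportionality could mislead that planning.

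**Working it through.** **Protocol's own figures (Table GZHA.2).** Predicted exposure at 0.15 mg is AUC 7670 ng·h/mL and Cmax 31.2 ng/mL. Scaling by 7.5/0.15 = 50 gives AUC 383,500 (stated 386,000, 0.7% apart) and Cmax 1560 (stated 1580, 1.3% apart). The protocol's prediction is therefore proportional to within rounding, and a true ratio of 1.00 is the natural reference.

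**Assumptions (not in the documents).** One-compartment first-order absorption; half-life 75 to 150 h; LLOQ 0.1 to 10 ng/mL; nominal sampling times; no between-subject noise. AUC(0-∞) uses the last three quantifiable points for the terminal slope.

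**Formulas.** C(t) = (dose/0.15) × 7670 × ka·ke/(ka − ke) × [exp(−ke·t) − exp(−ka·t)], with ke = ln 2/half-life and ka solved so that the peak at 0.15 mg is 31.2. This gives ka of 0.0136, 0.030, 0.060 and 0.124 per h at half-lives of 75, 113, 135 and 150 h. AUC is linear up to tmax and logarithmic after it, as in SAP 9.3.1. With b the slope of log AUC on log dose over the six doses, the 7.5 versus 0.15 mg dose-normalised ratio is 50^(b − 1).

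**Worked case: half-life 150 h, LLOQ 5.** At 0.15 mg the concentrations at 168, 336, 672 and 1008 h are 16.9, 7.79, 1.65 and 0.349 ng/mL. Scaling by dose gives tlast of 336, 672, 672, 1008, 1008 and 1008 h from lowest to highest dose. The observed fractions of total AUC are 0.776, 0.950, 0.950, 0.986, 0.986 and 0.986. Regressing their logs on log dose gives 0.598/11.03 = 0.0542, so the ratio is 50^0.0542 = 1.24.

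**AUC(0-tlast) ratio under exact proportionality**

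| LLOQ (ng/mL) | 75 h | 113 h | 135 h | 150 h |
|---|---|---|---|---|
| 0.1 | 1.007 | 1.000 | 1.000 | 1.000 |
| 0.5 | 1.109 | 1.023 | 1.025 | 1.032 |
| 1 | 1.103 | 1.163 | 1.037 | 1.032 |
| 2 | 1.156 | 1.163 | 1.206 | 1.236 |
| 5 | 1.157 | 1.222 | 1.288 | 1.237 |
| 10 | 1.645 | 1.727 | 1.777 | 1.851 |

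The ratio is not monotone in half-life, because whole samples drop in or out. Stepping the half-life by 1 h widens the range at LLOQ 2 to 5 to 1.12–1.31 and leaves the picture unchanged.

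**The other AUCs on the same profiles.** AUC(0-168 h) gives 1.00 throughout: the predicted 168 h concentration at 0.15 mg is 17 to 24 ng/mL, above every LLOQ in the table. It covers 52 to 55% of total AUC. AUC(0-∞) gives 0.95–1.00 up to LLOQ 5 and 0.72–1.00 at LLOQ 10. The extrapolated share at 0.15 mg is 15 to 22% at LLOQ 2 to 5 and 47 to 62% at LLOQ 10.

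**Against sampling noise.** A simulation with six participants per dose (600 runs per setting, assumed between-subject CV 15% / 30%) gives the chance that the 90% CI for the AUC(0-tlast) slope lies wholly above 1; the nominal value is 5%. It is 4.5% / 4.7% at LLOQ 0.1, 15% / 14% at 1, 75% / 27% at 2, 90% / 49% at 5 and 100% / 91% at 10. For AUC(0-168 h) it stays at about 4 to 6% up to LLOQ 10.

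**The case against.** The strongest reply is that the same SAP sentence already contains the remedy. Cmax does not depend on the window, and AUC(0-∞) stays close to 1 up to LLOQ 5. The SAP also reports the percentage extrapolated, flags values above 20% and allows a subinterval of doses, so a careful reader could see the truncation. This largely stands, and it rules out the inference that the plan has no valid proportionality measure. What remains is narrower. AUC(0-∞) becomes extrapolation-dependent at 0.15 mg, the dose that anchors the ratio, and AUC(0-tlast) is reported beside it with equal standing.

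A second reply is that the assay is probably good enough. Protocol 5.1 expects 0.5 mg IV to be adequately measurable over the sampling period, and Protocol 5.5 expects IV exposure close to or slightly above SC at that dose. If 0.5 mg SC were quantifiable at 1008 h, the LLOQ could be at most 0.0198 × 0.5/0.15 = 0.07 ng/mL at a 75 h half-life, or 0.349 × 0.5/0.15 = 1.16 at 150 h. The ratio would then be at most about 1.03. That is small against the simulated 90% CI half-width on the slope at LLOQ 0.1: 0.031 at CV 15% and 0.061 at CV 30%, or factors of 50^0.031 = 1.13 and 50^0.061 = 1.27. This is a fair reason to expect a small bias. It is an expectation, though, and no LLOQ is stated.

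A reader might also take Protocol 7.5 ("If PK exposures from the SC 0.5 mg dose yields largely concentrations below quantification") as a forecast that low doses will be unquantifiable. It is a contingency for choosing the IV dose. Predicted Cmax at 0.5 mg is 31.2 × 0.5/0.15 = 104 ng/mL, so that event would need an LLOQ far above those modelled here or exposures far below prediction.

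Finally, little rides on the result: PK is secondary, the study is not powered, and escalation rests primarily on safety data. That limits the priority of the point without removing it.

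**Conclusion.** The point holds as a conditional one. AUC(0-tlast) is in the power model, its window can lengthen with dose, and under proportionality the resulting bias can only be upward. Its size runs from negligible (1.00–1.01 at LLOQ 0.1 ng/mL) through 1.02–1.11 at 0.5, 1.03–1.16 at 1 and 1.16–1.29 at 2 to 5, to 1.65–1.85 at 10. These figures rest on assumed one-compartment profiles matched to the protocol's predictions, assumed half-lives and an assumed LLOQ.

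It would go too far to say that a proportional drug will look supra-proportional: with a sensitive assay it would not. The supported gap is that no AUC in the proportionality analysis is both observed and on a common window, although one is already derived. This is a low-cost improvement to a secondary analysis and does not make the planned analysis invalid.

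**What to change.** In SAP 9.3.2, add AUC(0-168 h) to the power model beside Cmax and AUC(0-∞). State that AUC(0-tlast) is supportive where tlast differs by dose, and tabulate tlast by dose so that this can be seen.

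The cost is a sentence or two in the SAP and one more model fit; no new samples or derivations are needed. Protocol 10.3.2.2 says only AUC, so the addition fits its wording.

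The downside is that AUC(0-168 h) covers only about half of the predicted total AUC and says little about dose-dependent late elimination. AUC(0-∞) should therefore stay. If tlast at the lowest dose proves to be before 168 h, AUC(0-168 h) would itself need extrapolation there, and this should be reported.
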